4.1.2 Handling of missing data

Participants who discontinue the study prematurely (i. e. drop out) will not be replaced.

All data will be presented in the participant data listing as they are recorded on the Case Report Form (CRF), i. e., partially missing data will appear as such.

For participants who permanently discontinue the study intervention, an EOT visit (...) should be performed as soon as the study intervention has been discontinued. If the decision to stop the study intervention early is taken during a site visit, this visit becomes the EOT visit. The FU visit should be performed as planned after the last dose.

In general, data collected at early discontinuation visits will be handled as follows: If a valid value is available from the EOT visit and if the assessment time is in accordance with one of the upcoming visit windows (see Section 8.4.1 for visit windows) and is not assessed later than three days after last study drug intake, this value will be assigned to the respective visit for analysis. Values assessed at FU visits after EOT visits due to early discontinuation will be summarized together with FU visits after regular EOT visits at Day 84 (Visit 7) unless specified otherwise.

The data handling of efficacy data which might deviate from the procedure described above depending on intercurrent events is described in Section 8.4.

If parts of the start or stop date of an AE are missing (day, month or year) the relative onset of the AE with respect to treatment start and/or the duration of the adverse event will not be calculated.

Adverse events will be considered as treatment-emergent if they occur after the first study intervention intake and until 7 (calendar) days after last study drug intake.

To determine if an AE is treatment-emergent in case of missing or incomplete dates the following rules will be applied considering a "worst case" scenario, i. e. if it is possible that the AE is treatment emergent it will be considered as treatment-emergent:

- If the date of AE start is completely missing, the AE will be considered as treatmentemergent unless the stop date (or other information) suggests otherwise
- If the day of AE start is missing, but the month and year is known, the AE will be considered as treatment-emergent if the month of AE start is between the month of treatment start and the month of treatment end date plus 7 days (both included), unless the stop date of the AE (or other information) suggests otherwise
- If the day and month of AE start are missing, but the year is known, the AE will be considered as treatment-emergent if the year of AE start is between the year of treatment start and the year of treatment end date plus 7 days (both included), unless the stop date (or other information) suggests otherwise.

To determine if a medication is prior, concomitant or posterior with respect to study intervention intake in case of missing or incomplete dates a "worst case" scenario will be applied, i. e. if it is possible that a medication is prior it will be considered prior, if it is possible that a medication is concomitant it will be considered concomitant, and if its possible that a medication is posterior it will be considered posterior.

To determine if a procedure is prior, concomitant or posterior with respect to study intervention intake in case of missing or incomplete dates a "worst case" scenario will be applied, i. e. if it is possible that a procedure is prior it will be considered prior, if it is possible that a procedure is concomitant it will be considered concomitant, and if its possible that a procedure is posterior it will be considered posterior (for definition of prior, concomitant and posterior medications and procedures, refer to Section 6.3).

Duration of atopic dermatitis will be calculated as follows if date parts of first diagnosis are missing: if the day and month of first diagnosis are missing the day will be imputed as 1st of July, if only the day of first diagnosis is missing it will be imputed as the 15th of the month.

4.2 Primary Endpoint Analysis

4.2.1 **Definition of Endpoint(s)**

The primary efficacy endpoint is achievement of 75% reduction from baseline in the Eczema Area and Severity Index (EASI 75 response) at Week 12 (Day 84).

The EASI score ranges from 0 to 72. The lower the EASI score the better the state of the participant with respect to severity and extent of AD symptoms.

The EASI is a ClinRO assessing the extent of AD at four body regions (head and neck, trunk and upper and lower extremities) by measuring the average severity of four clinical signs at each body region: (1) erythema, (2) induration/papulation, (3) excoriation, and (4) lichenification, each on a scale of 0 to 3 (Hanifin et al, 2001).

For scoring, the sum of these severity scores for each region is multiplied by a region score, a value of between 0 and 6 representing the percentage of skin affected by eczema, and finally weighted by a body region dependent multiplier (0.1 for head/neck; 0.3 for trunk, 0.2 for

upper extremities and 0.4 for lower extremities). This provides an EASI score per body region, with the final EASI score being the sum of the 4 region scores. The minimum EASI score is 0 and the maximum EASI score is 72, with a higher score indicating worse severity of AD. Further information and a scoring table can be found in Section 8.1.1.

4.2.2 Main Analytical Approach

The analysis of the primary efficacy endpoint on the PPS will be performed as follows (according to the primary estimand, refer to Section 1.1):

The impact of a potential use of rescue medication (TCSs or TCIs) or SoC for treatment of AD on the efficacy effect will be accounted for as follows:

If rescue medication is used between Day 56 (Visit 6) and Day 84 (Visit 7) (or end of treatment if before Day 84 (Visit 7)) or if SoC is used (at any time), the participant will be specified as a non-responder with respect to the EASI 75 response from the time the rescue medication or SoC medication is used. SoC medication use after early discontinuation due to other reasons not related to AD will not trigger the classification as non-responder for the following time points.

If a participant discontinues study intervention due to lack of efficacy at any time (e.g., due to an adverse event related to AD such as disease flare), the participant will also be specified as a non-responder with respect to EASI 75 response from the time of the discontinuation.

Otherwise, missing data - e.g. due to study intervention discontinuation due to other reasons such as reasons related to Covid-19 pandemic (individual reasons or prevention/logistic measures), withdrawal of consent not due to lack of efficacy or adverse events not related to AD - will be imputed using a multiple imputation approach based on logistic regression model.

Bayesian inference will be used to quantify the EASI 75 responder rates on Day 84 in the zabedosertib and placebo treatment group. For each treatment group a non-informative Beta(1,1) prior will be used. The Beta(1,1) prior produces a posterior distribution in the same distribution family, namely Beta(k+1,n-k+1) with k being the number of EASI 75 responders in the respective treatment group and n being the number of all participants in the respective treatment groups based on the posterior distributions of the EASI 75 response rate in both treatment groups will then be used to calculate the posterior probability $P(\pi_{BAY} > \pi_{Plac} \mid data)$. In addition, median and 80% and 95% credible intervals will be calculated based on the posterior distributions for the response rates in both treatment groups as well as for the difference between both treatment groups.

Code similar to the following will be used for the Bayesian analysis:

```
data test;
    call streaminit(1234);
    do i=1 to &simno.;
        *simulation BAY;
        p_bay=rand("beta", &k_bay.+1,&n_bay.-&k_bay.+1);
        *simulation Placebo;
        p_pla=rand("beta", &k_pla.+1,&n_pla.-&k_pla.+1);
        *counts for advantage for zabedosertib;
        diff = p bay - p pla;
```

end:

Version 1.0

```
if diff > 0 then count=1;
else count=0;
output;
```

run;

A seed of 1234 will be used and at least 100000 iterations will be performed.

The posterior probability for $P(\pi_{BAY} > \pi_{Plac} | data)$ will then be calculated as mean of count. The posterior distribution of the difference between the frequency of responders in the two treatment groups (diff) will be summarized by median, 2.5th and 97.5th percentile (95% credible interval) as well as 10th and 90th percentile (80% credible interval). The posterior distribution for the frequency of responders in the zabedosertib (p_bay) and placebo (p_pla) group will also be summarized by median, 2.5th and 97.5th percentile (95% credible interval) as well as 10th and 90th percentile (80% credible interval).

Histograms will be presented for the posterior distribution of achievement of EASI 75 response at Day 84 (Visit 7) for zabedosertib, placebo and the difference (zabedosertib – placebo) in Section 10 of the CSR.

Imputation of missing EASI 75 response information for Day 84 (Visit 7)

For a detailed technical description and data handling steps for the imputation of missing EASI 75 response information please also refer to Section 8.4.1 and 8.4.2. In the following the imputation procedure will be described in general:

In a first step imputation of missing EASI 75 response information will be done for all postdose visits according to the primary estimand as follows:

- Use of topical rescue medication: At Day 56 (Visit 6) or later (until Day 84 (Visit 7) or end of treatment if before Day 84 (Visit 7)): analyze study participant as non-responder (composite strategy)
 - Before Day 56 (Visit 6): disregard use of topical rescue medication (treatment policy strategy)
- Use of systemic standard of care: analyze study participant as non-responder (composite strategy) (SoC medication use after early discontinuation due to other reasons not related to AD will not trigger the classification as non-responder for the following time points.)
- Discontinuation of treatment due to lack of efficacy: analyze study participant as non-responder (composite strategy)

In the next step, imputation of still missing EASI 75 response information at Day 84 (Visit 7) will be done (in case of discontinuation of treatment due to reasons not related to lack of efficacy at Day 56 (Visit 6) or later or a missing Day 84 (Visit 7) EASI score) according to the primary estimand:

- Discontinuation of treatment due to reasons not related to lack of efficacy (including Covid-19 related reasons): At Day 56 (Visit 6) or later: imputation of response information (hypothetical strategy)
- Missing Day 84 (Visit 7) EASI assessment: imputation of response information using data from Day 56 (Visit 6) or later (hypothetical strategy), if

none of the conditions applies which are described above.

(If an imputation based on Day 56 (Visit 6) is not possible due to scarcity of data, imputation might be based on data from earlier time points or baseline only.)

In detail, the imputation will be done for the following participants in the PPS:

- with EASI score at baseline and Day 56 (Visit 6),
- without EASI 75 response information at Day 84 (Visit 7),
- without systemic SoC use before Day 56 (Visit 6) EASI score,
- without rescue medication use at Day 56 (Visit 6) EASI score.

The imputation for the primary analysis will be performed by treatment group using the monotone logistic regression method from the SAS multiple imputation procedure (PROC MI). A logistic regression model will be built based on the following participants in the PPS:

- with EASI score at baseline and Day 56 (Visit 6),
- with EASI 75 response information at Day 84 (Visit 7),
- without systemic SoC use before Day 56 (Visit 6) EASI score,
- without rescue medication use at Day 56 (Visit 6) EASI score,
- without rescue medication use (irrespectively of the indication) within the 7 days before the Day 56 (Visit 6) EASI score (to avoid influence of EASI scores directly after rescue medication on the imputation of the primary endpoint).

Participants with intercurrent event use of systemic SoC or rescue medication or discontinuation due to lack of efficacy after the Day 56 (Visit 6) EASI score and before Day 84 (Visit 7) will have EASI 75 response information (non-response) at Day 84 (Visit 7) and can be included in the logistic regression model if they fulfill the criteria specified above.

The EASI 75 response information at Day 84 (Visit 7) (coding: responder=1, non-responder=0) will be the dependent variable in the logistic regression model and the following variables will be included as independent variables:

- EASI score at baseline,
- EASI score at Day 56 (Visit 6).

If the multiple imputation using logistic regression as described above is based on less than 8 participants per treatment group the imputation with logistic regression as described above will be performed with the EASI score at baseline and at the previous visit as independent variable. If there will not be sufficient participants to include one of the post-dose visits (Day 28 (Visit 5), or – if not possible – Day 14 (Visit 4)) the logistic regression model will only use the EASI score at baseline as independent variable. Then the model will be based on all participants with EASI score at baseline and EASI 75 response at Day 84 (Visit 7) which might be imputed as non-response after SoC use, discontinuation of study intervention due to lack of efficacy or use of rescue medication after Day 56 (Visit 6). The variables used in the regression model will be indicated below the output table.

If there is a participant with rescue medication use within the 7 days before the Day 56 (Visit 6) EASI score and missing EASI 75 response at Day 84 (Visit 7) which needs to be imputed

the same procedure as described above (in case of less than 8 participants per treatment group) will be applied for that participant.

Imputation according to the procedure defined above will be performed 50 times. All participants with values imputed using logistic regression will be combined with the remaining participants (which will have the same values for each imputed dataset).

Bayesian analysis will then be performed based on all participants in the PPS as described above for each imputed dataset to generate posterior samples for the frequency of responders in the zabedosertib (p_bay) and placebo (p_pla) group and the difference (diff) between both.

As suggested by Zhou and Reiter (2010) the Bayesian posterior probability that the EASI 75 responder frequency after treatment with zabedosertib is higher than after placebo will then be derived based on the combined simulated posterior distribution (i. e. combining the posterior samples from all imputed datasets) of the difference in EASI 75 responder frequencies (zabedosertib – placebo). Medians, 80% and 95% credible intervals and histograms will be calculated based on the combined simulated posterior distribution as well. The same will be done for the EASI 75 responder frequencies in the zabedosertib and placebo group.

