 $\pi_{BAY} > \pi_{Plac}$ ('clinical activity' criterion),

i.e. that the EASI 75 responder rate after treatment with zabedosertib is higher than after placebo.

The study will be evaluated using Bayesian statistics, which allows to determine the posterior probability in favor of a hypothesis. Therefore, it is not needed to specify a pair of hypotheses. The statistical hypothesis will be considered accepted if the posterior probability for the hypothesis of interest is higher than 90%.

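### The primary posterior probability is simulated with an open-ended number of draws although it can be computed exactly; this matters only in rare outcomes very close to 0.90

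*SAP*

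**What the plan says.** The success rule in SAP Section 2 (Statistical Hypothesis) is a hard cut: "The statistical hypothesis will be considered accepted if the posterior probability for the hypothesis of interest is higher than 90" per cent. Protocol 9.1 has the same rule.

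SAP 4.2.2 sets up a conjugate analysis: "For each treatment group a non-informative Beta(1,1) prior will be used". The posterior in each arm is therefore a Beta distribution, "namely Beta(k+1,n-k+1) with k being the number of EASI 75 responders" and n the arm size. The SAP then draws from both posteriors, counts the draws in which zabedosertib has the higher rate, and states that the probability "will then be calculated as mean of count". On the simulation itself it says: "A seed of 1234 will be used and at least 100000 iterations will be performed". The program is introduced as indicative: "Code similar to the following will be used for the Bayesian analysis".

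Where responses are multiply imputed, the analysis is run on each of 50 completed data sets and the result is read from the stacked draws, "combining the posterior samples from all imputed datasets".

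The visible text gives no upper limit on the number of draws, no Monte Carlo tolerance, and no rule for an estimate close to 0.90. Protocol 9.3.2.1 also specifies simulation.

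**The concern.** Simulation is useful when a posterior probability has no convenient exact form. Here there are two independent Beta posteriors with integer parameters. The probability that one rate exceeds the other is then a finite sum, or a one-dimensional integral. Simulating it adds a random error to a number that is then compared with a fixed threshold.

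The seed is fixed, but the number of draws is a floor. A run of 100,000 draws and a longer run from the same seed both comply with the SAP and give slightly different estimates. In most outcomes this cannot matter. In an outcome that sits almost exactly on 0.90, the verdict on the trial's only formal criterion could depend on how many draws the programmer chose.

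**Working it through.** **Inputs.** Beta(1,1) priors, posterior Beta(k+1, n−k+1), at least 100,000 draws and 50 imputations (SAP 4.2.2); strict cut at 0.90 (SAP Section 2); 38 and 19 evaluable participants, response rates 0.49 and 0.16, power at least 90% (SAP Section 5). The rates 0.30 and 0.16 used below are my assumption for an intermediate effect.

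**Exact value.** Let zabedosertib have posterior Beta(a₁, b₁) and placebo Beta(a₂, b₂), all integers, and let B be the beta function. Then

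P(π_BAY > π_Plac) = Σ over i = 0 … a₁−1 of B(a₂+i, b₁+b₂) / [(b₁+i) · B(1+i, b₁) · B(a₂, b₂)].

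**1. The plan's own figure.** I evaluated this for all 39 × 20 = 780 possible outcomes and added the binomial probabilities of those above 0.90. Power at 0.49 versus 0.16 is 91.0%. A one-sided 10% normal approximation gives 90.8%. The stated power of at least 90% is reproduced.

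**2. The boundary outcome.** For 10/38 versus 2/19 the posteriors are Beta(11, 29) and Beta(3, 18). The sum gives 0.899987, and numerical integration agrees. The criterion is not met; the gap to 0.90 is 0.000013.

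**3. Monte Carlo error.** SE = √(P(1−P)/M), where M is the number of draws. The chance of falling on the wrong side of 0.90 is Φ(−|P−0.90|/SE).

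- M = 100,000: SE = √(0.9 × 0.1 / 100,000) = 0.00095.
- M = 50 × 100,000 = 5,000,000 independent draws: SE = 0.00013.

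| Outcome | Exact P | Wrong side, 100,000 draws | Wrong side, 5,000,000 independent draws |
|---|---|---|---|
| 10/38 vs 2/19 | 0.899987 | 49% | 46% |
| 21/38 vs 7/19 | 0.90040 | 34% | 0.2% |
| 19/38 vs 6/19 | 0.90067 | 24% | below 0.1% |
| 30/38 vs 12/19 | 0.89934 | 24% | below 0.1% |

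These four are the only outcomes within one SE of 0.90 at 100,000 draws. A fifth, 23/38 versus 8/19 (0.90247), lies within three SEs and has a 0.4% chance of the wrong side. In 1,000 simulated repeats of the 100,000-draw analysis at 10/38 versus 2/19, estimates ranged from 0.8969 to 0.9029 and half exceeded 0.90.

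**4. Overall effect.** Weighting each outcome's wrong-side chance by its binomial probability gives the chance that simulated and exact decisions differ:

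| True rates | 100,000 draws | 5,000,000 independent draws |
|---|---|---|
| 0.49 vs 0.16 (design) | 0.2% | 0.03% |
| 0.16 vs 0.16 (no effect) | 0.4% | 0.4% |
| 0.30 vs 0.16 (assumed) | 1.4% | 1.3% |

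In the last two rows almost all of the effect comes from 10/38 versus 2/19. That outcome has probability 0.055% at the design rates, 0.89% with no effect and 2.9% at 0.30 versus 0.16. At 0.16 versus 0.16, the exact rule is met 6.93% of the time; counting this outcome as a success makes it 6.93% + 0.89% = 7.82%.

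**5. Other arm sizes.** Different evaluable numbers put other outcomes near the cut. For example, 17/40 versus 5/20 is within 0.0005 of 0.90 and 13/38 versus 3/18 is within 0.0004.

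**The case against.** The strongest reply is that this is a programming detail. The study is exploratory, the result is reported with medians, two credible intervals and histograms, and posteriors of 0.8997 and 0.9003 carry the same evidence. Changing the prior to Jeffreys would move 10/38 versus 2/19 to 0.920, about 21 Monte Carlo SEs. All of this stands, and it is why the point is minor. It does not justify leaving removable noise in the one quantity that has a hard cut.

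Three stronger readings are tempting, and the documents do not support them.

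- *The fixed seed is the fault.* It is a safeguard: it makes a run reproducible and prevents a seed from being chosen after unblinding. The loose element is the open-ended number of draws.
- *Pooling 50 imputations cannot reduce the noise because the seed is reset for each set.* The program shown does contain "call streaminit(1234"), and resetting it per data set would give identical draws for data sets with identical counts. But the code is only indicative, the text does not say that the seed is reset, and the detailed imputation section (SAP 8.4.2) is redacted. The point stays conditional. Pooling also does not apply to the analyses that use non-response or last observation carried forward (SAP Table 4-1), which have a single completed data set.
- *The decision is at risk whenever the outcome lands near the cut.* The chance of landing within three SEs is 0.8% at 0.49 versus 0.16 and 2.9% at 0.30 versus 0.16. Those are not chances of a changed decision, which are 0.2% and 1.4%.

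Two objections to an exact calculation also have substance. First, imputation noise remains. If one zabedosertib response is missing and imputed with probability 0.5 (an assumption), the posterior against 2/19 alternates between 0.859 (9/38) and 0.900 (10/38). Over 50 imputations the resulting SE is 0.0413 × 0.5 / √50 = 0.0029, about three times 0.00095. Second, SAP 4.8 adds the 80% interval to match the success criterion, so an exact decision beside a simulated interval could disagree on the boundary. The fix has to cover the interval as well.

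**Conclusion.** The point holds as a minor, nearly free improvement. The primary probability is exactly computable in each completed data set. The SAP simulates it with an unspecified number of draws, and at the planned arm sizes one outcome (10/38 versus 2/19) cannot be classified reliably even with 5,000,000 independent draws. The chance that this changes the trial's decision at 100,000 draws is about 0.2% under the design assumptions and about 1.4% at an assumed 30% versus 16%. The stated power is unaffected.

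These figures assume 38 and 19 evaluable participants, complete responses, and simulation error that is approximately normal. It would be wrong to conclude that the result depends on the seed rather than on the data: only about the third decimal of the probability is random, and that matters in a handful of the 780 possible outcomes.

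**What to change.** Before unblinding:

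1. Compute the probability by the closed-form sum or by numerical integration for each imputed data set, average over the 50 sets, and compare the average with 0.90. This average is what stacking equal numbers of draws estimates. Analyses without multiple imputation need one evaluation.
2. Obtain the 80% interval limits for the difference numerically from the same mixture of posteriors, so that interval and decision agree.
3. Keep simulation for the histograms.
4. Record the change in SAP 4.8, since Protocol 9.3.2.1 specifies simulation.

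The cost is a few lines of SAS. Random error from the imputation itself is not removed.

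The minimum alternative is to state the exact number of draws and use one continuous random stream across the imputed data sets. That makes the verdict unique for a given program, but it leaves the simulation error in place.

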4.8 Changes to Protocol-planned Analyses

According to the protocol a blinded monitoring of sample size assumptions was planned. This monitoring will not be applied because on the one hand the recruitment period turned out to be quite short (approximately 5 months) while on the other hand the study duration for a single participant is quite long (approximately 5 months). There is sufficient confidence in assumptions for sample size to go without further monitoring.

For the bayesian analysis of primary and binary secondary endpoints 80% and 95% credible intervals will be listed instead of 90 and 95% credible intervals to add one confidence interval corresponding to the clinical activity criterion.

5. Sample Size Determination

A Bayesian concept will be used for inference, which is based on the posterior probability that the research hypothesis is true. Therefore, it is the goal of this study to demonstrate that zabedosertib is superior to placebo with posterior probability > 90%, i.e. $P(\pi_{BAY} > \pi_{Plac} | data) > 90\%$ (='clinical activity' criterion).

The EASI 75 responder rate of 0.49 for assumed systemic standard of care (SoC) dupilumab was derived as the mean responder rate from a meta-analysis on the active treatment arms in two Phase 3 AD studies (Simpson et al, 2017), comprising 919 participants.

Non-informative Beta(1,1) priors will be used for the Bayesian inference.

For Placebo, a response rate of 16% was assumed. The statistical power was determined with SAS 9.4.

Assuming that the EASI 75 responder rate in zabedosertib-treated participants is 0.49, evaluable data from 57 participants (38 on zabedosertib, 19 on placebo) will provide at least 90% power to establish superiority of zabedosertib. Approximately 72 participants will be randomly assigned to the study to obtain 57 evaluable participants overall (2:1 randomization zabedosertib versus placebo).

6. Supporting Documentation

The number of participants enrolled, randomized and valid for the SAF, PPS, FAS, PKS, BAS will be summarized for each study site and overall. The number of participants randomized, and the number of sites will further be summarized by country. The number of participants with important protocol deviations and the number of screen failures will be summarized by country and study site.

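### Averaging the primary posterior probability over only 50 imputed datasets leaves avoidable Monte Carlo noise at the 90% cut: about ±1.5 points if five or six Day 84 responses are imputed, with a small overall chance of changing the decision

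*SAP*

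**What the plan says.** SAP Section 4.2.2 imputes missing Day 84 EASI 75 response within each arm by logistic regression on baseline and Day 56 EASI. On the number of imputations it says "Imputation according to the procedure defined above will be performed 50 times". The Beta-binomial analysis is run on every imputed dataset, and the decision probability comes from "combining the posterior samples from all imputed datasets". On the simulation within a dataset it says "A seed of 1234 will be used and at least 100000 iterations will be performed".

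SAP Section 2 gives the decision rule: the hypothesis is accepted "if the posterior probability for the hypothesis of interest is higher than 90" per cent. SAP Section 4.3.2 applies the same approach to the binary secondary endpoints.

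The readable text gives no reason for choosing 50, no Monte Carlo error for the imputation step and no expected number of missing Day 84 responses. The detailed technical description in Section 8.4.2 is blacked out, so nothing is inferred from its absence.

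**The concern.** Every dataset contributes the same number of draws, so pooling them is the same as averaging 50 per-dataset probabilities. Each of those depends on the imputed responder counts. With 19 evaluable placebo participants planned, one imputed placebo responder can move the probability by more than ten points. The error of the average is the between-imputation standard deviation divided by √50, however precisely each dataset is evaluated. The plan therefore spends its precision on the posterior draws, which matter less, and leaves the imputation step coarse.

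At stake is the trial's only formal success criterion. If the pooled probability lies within a point or two of 90%, the outcome could depend on which 50 imputations happened to be drawn.

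**Working it through.** **Inputs from the documents.** 50 imputations, at least 100,000 draws per dataset, mixing of draws (SAP 4.2.2); cut above 0.90 (SAP 2); Beta(1,1) priors, 38 and 19 evaluable participants, assumed rates 0.49 and 0.16, at least 90% power (SAP 5). **Assumed, because not given:** the number of imputed Day 84 responses (one to nine, written zabedosertib + placebo) and the imputation probabilities.

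**1. The plan's own figure.** Enumerating every pair of responder counts at 38 and 19, with the exact P(π_BAY > π_Plac) for Beta(k+1, n−k+1) posteriors, gives 91.0% power. The stated figure reproduces.

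**2. Noise from posterior draws.** At 0.90 the 95% half-width is 1.96 × √(0.90 × 0.10 / draws). This is ±0.19 points with 100,000 draws and ±0.03 with 50 × 100,000 = 5 million.

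**3. Noise from imputation, one worked case.** Observed: 10 responders of 35 on zabedosertib with 3 missing, and 2 of 17 on placebo with 2 missing. Imputation probabilities are 0.35 and 0.15. Exact probability for each imputed count:

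| Imputed responders, zabedosertib | placebo 0 | placebo 1 | placebo 2 |
|---|---|---|---|
| 0 | 0.900 | 0.787 | 0.638 |
| 1 | 0.931 | 0.841 | 0.712 |
| 2 | 0.953 | 0.885 | 0.776 |
| 3 | 0.969 | 0.918 | 0.830 |

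With binomial weights the mean is 0.9017 and the between-imputation SD is 0.0557. The standard error at 50 imputations is 0.0557/√50 = 0.0079, so the half-width is 1.96 × 0.79 = ±1.5 points. At 1,000 the standard error is 0.0018 (±0.35 points) and at 2,000 it is 0.0012 (±0.24 points).

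**4. Dependence on the number imputed.** 95% half-width in points at 50 imputations, for pooled probabilities of 0.87 to 0.93. The first column enumerates fixed imputation probabilities (0.16 to 0.50). The second simulates arm-wise logistic imputation with coefficient draws, at an assumed Day 56/Day 84 correlation of 0.5 or 0.8.

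| Imputed | Enumeration: median (range) | Logistic: median at 0.5 / 0.8 |
|---|---|---|
| 1+0 | 0.42 (0.25–0.57) | not run |
| 1+1 | 1.11 (0.70–1.55) | 0.95 / 0.93 |
| 2+1 | 1.11 (0.72–1.54) | 1.06 / 0.90 |
| 3+2 | 1.46 (1.04–2.14) | 1.45 / 1.34 |
| 4+2 | 1.58 (1.03–2.21) | 1.51 / 1.32 |
| 6+3 | 1.83 (1.29–2.55) | 1.99 / 1.83 |

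**5. Chance of a changed decision.** For each possible outcome, the chance that 50 imputations decide differently from infinitely many is Φ(−|mean − 0.90| / SE). This was weighted by the probability of that outcome, for 1+0 to 4+2 imputed:

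- design rates 0.49 and 0.16: 0.01% to 1.1% (1.1% with 3+2 imputed);
- weaker effect, 0.30 and 0.16 (assumed): about 0.1% to 1.8%;
- no effect, 0.16 in both arms: 0% to about 1%.

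**The case against.** **The number imputed may be small.** This stands. The per-protocol set drops participants without an EASI at Day 56 or later unless they already count as non-responders. Rescue from Day 56, systemic standard of care and discontinuation for lack of efficacy become non-response without any random draw. The Day 84 analysis window runs from Day 76 to Day 92 and can be filled from unscheduled or end-of-treatment visits. The ±1.5 points is therefore conditional on the number imputed.

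**A result near the cut is uncommon.** This also stands. A reader might infer from the worked case that the decision is close to a coin toss: there the 50-imputation value falls below 0.90 about 42% of the time, since Φ((0.9000 − 0.90165)/0.00787) = 0.42. But that case sits only 0.17 points above the cut. With a limiting value of 0.887 (same observed counts, imputation probabilities 0.30 and 0.20), 50 imputations cross 0.90 in 6.7% of runs. Across all outcomes the chance of a change is that in step 5.

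**The study is exploratory and sensitivity analyses exist.** SAP Section 2.1 calls it exploratory, and Section 4.2.3 repeats the analysis with non-response and last observation carried forward, neither of which uses random imputation. They give useful context for a borderline result, but they answer different questions and do not sharpen the primary figure.

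**A fixed seed would settle it.** A seed makes the result repeatable, not less noisy. With Section 8.4.2 unreadable, no view is taken on whether an imputation seed is given.

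**Conclusion.** The point holds as a matter of precision. If about five or six responses are imputed, two on placebo, a pooled probability near 90% carries a 95% half-width of about ±1.5 points (standard error about 0.75). It is about ±0.4 to ±1.1 with one to three imputed, about ±1.8 to ±2.0 with nine, and zero with none. Only more imputations, or exact averaging over the imputed counts, reduce it.

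A reader might infer that the primary result is biased or that the decision rule is unreliable. The documents do not support either. The average is centred on the right value for the stated model, the power claim reproduces, and the chance of a changed decision was about 2% or less in every scenario enumerated (up to six imputed). All these sizes rest on assumed numbers of missing responses and assumed imputation probabilities.

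**What to change.** Before treatment codes are opened, which under SAP Section 4.7 first happens at the administrative interim analysis:

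- Raise the number of imputations for the primary and binary secondary endpoints from 50 to at least 1,000 to 2,000. In the worked case this brings the half-width to about ±0.35 to ±0.24 points.
- Compute each dataset's probability exactly from its two Beta posteriors, or cut the draws per dataset. At 2,000 imputations, keeping 100,000 draws would mean 200 million pooled draws per endpoint instead of 5 million. Using 2,500 draws per dataset keeps the pooled total at 5 million for the medians and credible intervals.
- Report the Monte Carlo standard error of the probability across imputations (between-imputation SD divided by the square root of the number of imputations) beside the result.

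The cost is a small program change and slightly more computing. No estimand, imputation model, analysis set or threshold changes. Fixing the number in advance also avoids any question of choosing it after seeing a borderline result.
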